## Program Descriptions

### Control Participants: General Health Videos

Participants in the control arm will receive a general health education DVD and handout. The DVD contains videos on the following topics: Dementia and Alzheimer's, Breast Cancer, Colorectal Cancer, Osteoporosis and Fall Prevention, Eye Health, Oral Health, Foot Care, and Driving Safety. A copy of the handout is included as Appendix A.

### Intervention Participants: Living Well with Diabetes

#### *Peer Advisors Recruitment*

Peer advisors are individuals who live and work in our target communities. Peer advisors are hired by Health and Wellness Education Center in Livingston Alabama. Peer advisors will be trained in motivational interviewing, basics of communication and goal setting. In addition, peer advisors will complete an 8-week study protocol training supervised by [name] of Health and Wellness Education Center and lead by [name] and study staff.

Peer advisor candidates are recruited by 3 methods.

1. Community coordinators identify individuals in their community or social networks who they believe would be great peer advisors.
2. Current peer advisors refer individuals from their communities or social networks.
3. Participants of previous studies with peer advisors express interest in being a peer advisor.

After an individual is referred, UAB staff or the local community coordinator completes a Peer Advisor Candidate Screening Form (see Appendix B).

After the screening form is completed, the principal investigator, community coordinator, study coordinator, and the UAB staff (who completed the screener) meet to review the form and discuss each candidate.

- If the candidate is not asked to move forward in the training, the reason is documented. These individuals are notified in person by the community coordinator.
- If the individual is considered to be a good candidate but is unavailable for the scheduled training, permission is obtained from the individual to contact them for future programs.
- Individuals who are considered a good candidate to a be peer advisor is scheduled for an upcoming training.

#### *Peer Advisor Retention*

As is the recruitment efforts, peer advisor retention efforts will be coordinated between UAB Birmingham-based staff, UAB community-based staff (community coordinators), and the Health and Wellness Education Center. Retention activities consist of the following:

1. Ensure timely payment for work
2. Provide ongoing support and continuing education/retraining with opportunities for practicing skills
  - a. UAB Birmingham staff: Weekly group conference calls
  - b. UAB Birmingham staff: Weekly individual calls to collect process measures, monitor progress

- c. Community coordinator: weekly individual contact to provide support, identify issues early
  - d. Provide support and identify ways to reduce/help with workload during periods of stress in peer's lives.
3. Be respectful of peer advisors' time and schedules
    - a. Keep mandatory conference calls and individual calls on time, short as possible, and reschedule only if necessary.
    - b. Provide assistance as needed in scheduling sessions with participants
  4. Recognize and thank peers for their work
    - a. Holiday celebrations:
      - i. face-to-face dinner or lunch 1-2 times per year
      - ii. send notes/cards for birthdays and holidays
    - b. Identify ways to celebrate in the local media the peer advisor's work in the community
  5. Engage peers in leading and presenting for other community activities (ex: Black Belt Institute, Coalition meetings, and as opportunities become available)

### ***Living Well with Diabetes Program Description***

Participants enrolled in the intervention arm will receive a Living Well DVD, which contains 6 video lessons that cover 6 content areas (1-diabetes basics, 2-healthy eating, 3-physical activity, 4-diabetes medications, 5-blood pressure & cholesterol medications, and 6-stress and your health), and an Activity Workbook. The participant will use the activity book when communicating with their peer advisors during the sessions.

Every session, the peer and participant will discuss the participant's medication goals. During week 1, the participant will set a medication related goal. During week 2, the participant will set a goal related to healthy eating. During week 3, the participant will set a goal related to exercise. The peer and participant will review the previous week's goal and progress of the goal. If the participant met the goal and ready to extend the goal, the peer advisor will help the participant set a new goal. If session has a video, the peer and participant will discuss the educational content in the video.

During the check-in sessions, no new topic areas are introduced. The peer advisor will review the previous week's goals. Peer will review goal's progress and assess barriers and help problem solve any barriers. New goals will be set if the participant is ready to extend the goal.

### **Intervention participants also receive 13-16 telephone contacts from a Peer Advisor.**

Months 1-3 are the intensive phase. During the first 8 weeks of the intensive phase, peer advisor contacts will occur weekly. During weeks 9-12, the peer contact will occur bi-weekly.

Months 3-6 are the maintenance phase. During this phase, the peer contacts will occur monthly. No new content areas are introduced. Participant will continue to work on the goals set during the first 3 months of the program. The peer advisor will call monthly during the "check-in session". During these sessions, the peer and participant will review goals set, goal progress, assess barriers and help problem solve barriers. If participant is having trouble with their health goals during this phase, the peer and participant can decide that more contacts than monthly contacts are needed. For these participants, the peer advisor will provide a 'mini-intensive' phase, during which calls will be increased to weekly.

The participants will be allowed to telephone the peer advisors with questions or concerns between sessions. During session 1, the peer advisor makes sure that the participant has the correct contact number. The peer will let the participant know that it's okay to call between sessions if they have questions. They will let them know that they may not be able to take the participant calls all the time, but the peer will return their calls as soon as they can.

The schedule and topics for each week are listed below.

Mon	Week	Session Topic	Mon	Week	Session Topic
1	1	Introduction to the program, diabetes basics	4	13	No session*
	2	Healthy eating		14	No session*
	3	Physical activity		15	No session*
	4	Diabetes medications		16	Check-in session 3 (no new topic)
2	5	Blood pressure & cholesterol medications	5	17	No session*
	6	Stress and your health		18	No session*
	7	Check-in session 1 (no new topic)		19	No session*
	8	Practice and planning for the future, part 1		20	Check-in session 4 (no new topic)
3	9	No session	6	21	No session*
	10	Check-in session 2 (no new topic)		22	No session*
	11	No session		23	No session*
	12	Practice and planning for the future, part 2		24	Check-in session 5 (no new topic)

*Months 1-3 = Intensive phase; Weeks 1-8 weekly contact; weeks 9-12 biweekly contact*

*Months 4-6 = Maintenance phase; monthly contacts*

*\*The last 3 months of the program is the maintenance phase during which no new content areas are introduced. The participant continues to work on the goals (3 goals – 1) goal to overcome barriers to taking medications, 2) health eating goal, 3) exercise goal) set during the first 3 months of the program. The Peer Advisor will check in with the participant monthly. If participant is having trouble with their health goals during this phase, the peer and participant can decide that more contacts than monthly contacts are needed. For these participants, the peer advisor will provide a ‘mini-intensive’ phase, during which calls will be increased to weekly.*

*Copies of the tools used by the peer advisors (Peer Advisor Manual and Client Plan Book) and participants’ Activity Book are included in Appendix C.*

## Recruitment of Participants

We will use respondent-driven sampling for recruitment. Flyers and interest cards are distributed by the community coordinators to their recruitment team. Flyers include the general purpose of the study and inclusion and exclusion criteria. Interested individuals sign an interest card with their contact information, which is forwarded to the research team based in Birmingham.

Prospective participants are screened for eligibility by a member of the research team over the telephone. Adults age >18 years with type 2 diabetes who respond “yes” to any question on the 4-item Morisky scale who are willing to watch a DVD and work with a peer coach to improve their diabetes self-care will be eligible for the study. Exclusion criteria include nursing home residence, plans to move away in the next year, and advanced illnesses such as hemodialysis, cancer or dementia. *The participant eligibility screening script is included in appendix D.*

### Recruitment Methods

Participants will be recruited by 4 methods.

1. Community member calls UAB after seeing an advertisement (i.e., radio ad, newspaper ad, flyers, heard about the study at a community event or community meeting)
2. Community recruiter
  - a. Individuals calls UAB after hearing about the study from a recruiter
  - b. Individual completes a participant interest card and the card is submitted to a community coordinator
3. Community Coordinator
  - a. Have individuals complete interest cards
  - b. Collects interest cards from community recruiters.
  - c. Collects interest cards from primary care practices / community organizations who recruit
4. Primary care practices
  - a. Flyers will be posted in local partner practices.
  - b. Research assistant in the waiting room

Community Recruiters. Community recruiters have been identified the community coordinators or peer advisors. Recruiters are asked to identify individuals in their social networks that may be interested in participating in a study to help them better care for their diabetes. Before they begin recruitment, community recruiters are given an orientation by the community coordinator and if needed, study coordinator. The recruiters are provided instructions and a checklist on how to complete the information sheet.

Community recruiter submits interest cards to their community coordinator who submits the cards to UAB staff. The community coordinator meets each community recruiter at minimum 1 time per week to arrange card pick-ups.

Community Coordinators. Community coordinators present the study to groups at local community events, health fairs, churches, etc. The individuals that they recruit complete an interest card or are asked to call the study’s phone number.

During weekly calls, coordinators and study staff discuss upcoming opportunities in the communities to recruit participants for the study. A recruitment calendar is maintained with the event’s name, the date and time, and the responsible study member who is attending the event.

Community coordinators also coordinate these following recruitment activities: radio announcements, putting up flyers, newspaper ads, church announcements, and working with local primary care providers.

Community coordinators or recruiter will call us with the individual's name and submit the interest cards. UAB staff will add the names to the recruitment tracking log.

For every individual referred that enrolls in the study, community recruiters receive a \$5.00 VISA gift cards. These cards are bundled and sent periodically.

Recruitment at Primary Care Practices. Passive recruitment at practices will consist of flyers posted in primary care practices in the local communities. Interest cards and interest card boxes will be placed in secure and monitored locations. Community coordinators will check-in with the practices and the boxes at minimum once per week.

Active recruitment at willing practice via site visits by UAB research staff. As practice schedules allows, research assistant or community coordinators will sit in the waiting room of the practice. Practice staff will walk interested patients to the research assistant who will present the study and complete the screening if the participant is interested in the study. The community coordinator will arrange for specific days in which the research assistants can visit the practices.

Recruitment Flyer is included in appendix D.

## **Eligibility Screening**

After the potential participants sign the interest card or call UAB, study staff will conduct an eligibility screening over the telephone using the "Telephone Eligibility Screening Script" in appendix D. If individuals are eligible for the study and interested in enrolling in the study, he or she will be scheduled for the telephone interview.

## Study Enrollment, Informed Consent, and Data Collection

### Telephone Interview

A waiver of documentation of informed consent for the telephone interview has been approved. The potential participant will be mailed the informed consent form that will be reviewed prior to the interview. The telephone interviews will be scheduled at the earliest date and time after the screening interview that the participant is available, allowing for 2-3 days needed for the participant to receive the informed consent document in the mail. Trained UAB study staff members will conduct the telephone interviews.

The telephone interview will begin with the interviewer reviewing the informed consent form with the participant. If the participant agrees to participate in the study, the interviewer will complete the baseline assessments.

Telephone interview is included in appendix E.

Interviews will be completed in the Preventive Medicine Research 510 suite. As such, the program coordinator and/or data coordinator will listen to interviews in progress. Furthermore, a random selection of interviews will be quality checked. For these interviews, the program coordinator or data coordinator will listen in to the entire interview.

## In-Person Biometric Data Collection Visit

After the interview is completed, the in-person data collection visit will be scheduled. Participants will be given the option of meeting at a community location or have UAB staff members come into the home to collect biometric data. Community locations most convenient for the participants and have private spaces available will be selected. Example locations include private rooms in community centers and church meeting rooms. UAB staff members, trained in the biometric study protocols will attend the biometric data collections. Data collectors for the study are trained and certified by study investigators. Training and certification for each data collection component are outlined in the biometric protocol. In summary, the data collector to be trained and certified, the following is necessary:

1. Read the biometric protocol (*Biometric protocol included in appendix F.*)
2. Attend Living Well training session on techniques
3. Practice on other staff or volunteers
4. To be certified, complete exam on 2 volunteers, observed by study investigator

During the screening, participants will be asked not to not drink any caffeine (from coffee, tea, or soda), should not eat or do any heavy physical activity, smoke, ingest alcohol for 30 minutes prior to recording the blood pressure.

During the in-person data collection visit, the participant will sign the informed consent. The following measures are collected during this visit: hemoglobin a1c, LDL-cholesterol, blood pressure, weight, and height.

Hemoglobin A1c will be measured using the A1cNow+ system, National Glycohemoglobin Standardization Program Certified, CLIA-waived system that provides Hba1c results using a fingerstick test.

LDL-Cholesterol will be measured using the Cardiochek PA analyzer, CLIA-waived system that provides LDL cholesterol results using a fingerstick test.

Blood pressures will be measured using the following protocol. Patient will be asked to sit quietly for 5 minutes. 2 BP measures, using an automated BP machine, will be taken. Measures will be taken 1 minute apart.

Data will be collected in this order.

1. Blood pressure:
  - a. 5 minute rest
  - b. blood pressure measurement 1 taken
  - c. 1 minute rest
  - d. blood pressure measure 2 taken
2. Fingerstick for A1c and LDL cholesterol measurements
  - a. A1c measured using the A1cNow+ machine
  - b. LDL cholesterol measured using the Cardiochek PA analyzer
3. During this visit, we will also make a list of all medications the participant is currently taking.
4. Provide participant with health report card

After the completion of the in-person data collection, the participant will be given the materials for the program. If the participant is in the control condition, they will be given a general health education DVD. Participants in the intervention condition will be matched with their peer advisor and given an activity book that they will use during their sessions with their peer advisors. All participants will receive their portable DVD player at the end of the data collection visit. Participants will receive a Health Report Card that provides their a1c, LDL-cholesterol, blood pressure, and weight data. If needed, participant in the intervention arm will receive a study phone.

Participants will be asked by the research staff at the in person data collection visit if they would like to use a study phone. Study phones will be taken back at the 2nd in-person study visit. Copies of the consent, in-person data collection form, and Health report card are included in Appendix F.

## Participant Compensation

Participants will receive a portable DVD player and a \$20.00 VISA giftcard. Participants will receive the DVD player at the first in-person data collection visit and the giftcard at the second in-person data collection visit.

[figure not shown]
## Participant Retention

During the 6 months of the trial, UAB staff will contact all participants 2-3 times. During these brief 5-minute calls, the staff will answer participant questions, update contact information, and provide help if needed in accessing study education materials. Participant retention plan will be a mixture of telephone and mail contacts as shown below:

Month	Control Participants	Month	Intervention Participants
1	Phone Call: Welcome to the study, answer questions	1	No contact
2	Postcard: Reminder to look at videos	2	Phone Call: answer questions, identify problems, update contact information
3	Phone Call: answer questions, identify problems, update contact information	3	No contact
4	Postcard: Keep in touch post card card	4	No contact
5	Phone Call: answer questions, identify problems, update contact information	5	Phone Call: answer questions, identify problems, update contact information
6	Postcard: reminder of upcoming data collection	6	No contact
All participants will receive postcards for birthdays, holiday cards (Thanksgiving, Christmas)			

During month 6 (control participants) or after the final session with the peer advisor (intervention participants), study staff will contact the participant to schedule their follow-up telephone interview and in-person data collection. Copies of postcards and telephone contact scripts are included in Appendix G.

The figure below shows the study flow from recruitment to the completion of the study.

LivingWell-FlowChart-v.2016-01-12

## Analysis

### Data management

Data is being entered into a Redcap Database. Validity checks and skip patterns maximize the quality of data entry and text entry is minimized. In-home visit data will be transcribed onto a form during the visit and faxed daily to the UAB research office. A tracking system will be implemented to monitor study progress using Redcap.

### Power Calculations and Sample Size

This study is powered to detect clinically meaningful differences in changes in medication adherence, A1c, blood pressure and LDL-cholesterol between either of the intervention arms compared with the usual care arm. The secondary outcomes are based on surveys (disease acceptance, quality of life). To consider the clustering of patients within town, we used a variance inflation factor  $D = [1 + \rho(m - 1)]$ , where  $m$  is the number of participants per community and  $\rho$  is the intra-class correlation (ICC). We conservatively estimate that we will have at least 80 clusters, corresponding to an average of 6-8 participants per cluster, with ICC=0.01 and 0.05 yielding  $D=1.084$  and  $1.419$ , respectively. Dividing the sample size per group  $N$  by  $D$  gives  $N_{\text{EFF}}$ , the effective sample size. In the Encourage study, those reporting nonadherence at baseline demonstrated ICCs in the range of 0.001-0.015 for most measures. To be conservative because we include new communities, we present power calculations for ICC=0.01-0.05. We observed 20% attrition over one year in the Encourage study and although attrition is likely to be lower over 6 months, we assume 20% attrition here, leaving 200 participants per group. Table 7 displays the detectable differences in adherence proportions and the difference in mean changes between groups detectable with 80% power using 2-sided  $X^2$  and t-tests with  $\alpha=0.05$ . We used variances based on the Encourage sample reporting nonadherence at baseline. We hypothesize that the intervention will result in improved medication adherence. Because eligibility requires low adherence at baseline, we expect low acceptance at baseline. Starting with low baseline values by design eliminates ceiling effects and allows us to reasonably anticipate large changes in the intervention groups and only modest changes in the control arm, as was seen in a storytelling intervention directed at blood pressure. For  $N=200$  per group, the difference in rates of medication adherence treated as a binary outcome detectable with 80% power depends on the proportion observed in the intervention group. If adherence is only 20% in the intervention group, then we can detect as different rates among the control group of 8.8-10.1%, depending on ICC. These rates are both lower than we anticipate for the intervention group and considerably higher than we expect in the control group. Assuming 200 participants per group we will have 80% power using 2-sided t-tests to detect differences of 0.28-0.32 standard deviations for continuous outcomes. Using variance estimates from Encourage data for change in the Diabetes Distress Score, another validated psychometric instrument, this translates into detecting differences as small as 3.7-4.4% of the range. Similarly, detectable differences for change in A1c are in a clinically meaningful range from 0.41-0.48%. We anticipate detectable differences for systolic blood pressure of 3-4 mmHg, and for LDL-cholesterol of 6.7-8.1 mg/dL.

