**Technical merit. Project Overview.** We will build on our ongoing partnerships with people living in Alabama's Black Belt, learning together how to improve outcomes for individuals with diabetes. In the first year of the study we will conduct focus groups with people with diabetes and medication nonadherence to learn more about their beliefs and attitudes toward living with diabetes and the medications used to treat the disease. Using this information and working within the Corbin and Strauss framework, we will collaboratively create DVDs of peer storytelling integrated into a diabetes education experience, and the peer coaching protocol, drawing on Social Cognitive Theory and Adult Learning Theory. We will pilot test the intervention, and we will implement the randomized controlled trial (RCT) comparing the effectiveness of the intervention with usual care. In years 2 and 3, we will recruit 500 individuals with diabetes who report medication nonadherence, group randomize them to one of the 2 trial arms, and collect baseline and follow-up data 6 months later. Control patients will receive comprehensive diabetes education on conclusion of the 6 month period. During all 3 years, we will also work with community coalitions in our partnering communities to obtain ongoing input, share knowledge of community resources, create a resource bank website to facilitate the peer coaches' work, and plan for dissemination of the interventions.

Figure 3. Partnering communities in the Alabama Black Belt: North ([name]), Western ([name]), South Central ([name]).

**The setting and our partnership.** Booker T. Washington described the Black Belt as “a part of the country which was distinguished by the colour of the soil. The part of the country possessing this thick, dark, and naturally rich soil was, of course, the part of the South where the slaves were most profitable, and consequently they were taken there in the largest numbers. Later and especially since the (Civil) war, the term seems to be used wholly in a political sense—that is, to designate the counties where the black people outnumber the white.” The Black Belt runs in an arc across central Texas up to Maryland. In Alabama, it is a 200-mile wide belt across the southern half of the state (Figure 3).

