**Aim 2:** Conduct a randomized controlled trial with 500 individuals with type 2 diabetes and medication nonadherence. The trial will compare the effect of usual care and the intervention on medication adherence and physiologic risk factors including A1c, blood pressure and low density lipoprotein cholesterol (primary outcomes), and quality of life and self-efficacy (secondary outcomes).

This innovative approach would be a major shift in how we help patients in under resourced areas living with chronic diseases commit to taking medications, improving health and eventually reducing health disparities.

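### The printed design effects do not fit the stated 6-8 participants per town, and at 200 per group the detectable differences do not follow from them

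*Combined protocol and SAP*

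**What the plan says.** The section Power Calculations and Sample Size inflates the variance for clustering by town with D = 1 + ρ(m − 1). It assumes at least 80 towns, "corresponding to an average of 6-8 participants per cluster, with ICC=0.01 and 0.05 yielding" D = 1.084 and 1.419. After 20% attrition it has 200 participants per group.

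For continuous outcomes it says that "we will have 80% power using 2-sided t-tests to detect differences of 0.28-0.32 standard deviations for continuous outcomes". For adherence it takes 20% in the intervention group and says "then we can detect as different rates among the control group of 8.8-10.1%, depending on ICC". It then gives detectable ranges for A1c (0.41-0.48%), systolic pressure (3-4 mmHg), LDL-cholesterol (6.7-8.1 mg/dL) and diabetes distress (3.7-4.4% of the range). It prints no SD for any of these.

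The section opens by claiming power for comparisons "between either of the intervention arms compared with the usual care arm". Elsewhere the design has one intervention arm. Aim 2 reads "Conduct a randomized controlled trial with 500 individuals with type 2 diabetes", and the project overview in the Background says the team will "group randomize them to one of the 2 trial arms".

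**The concern.** The formula, the cluster size and the ICCs are all printed, so D can be checked directly, and it does not come out. The detectable differences can be checked in turn from D and 200 per group, and they do not come out either. The wording about more than one intervention arm suggests that some figures belong to another design.

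This is the only sample-size justification in the documents. It covers binary adherence, which the Data Analysis section makes the primary analysis, and the A1c, blood pressure and LDL outcomes. If the figures do not share one set of inputs, a reader cannot tell which differences the trial can detect with 80% power.

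**Working it through.** **Inputs.** Two-sided α = 0.05, power 80%, 200 analysed per group, ICC 0.01 and 0.05, at least 80 towns, m = 6-8, and the printed D values (all from Power Calculations and Sample Size). Total of 500 from Study Aims; two arms from the Background project overview. 500 × 0.8 / 2 = 200, so 1:1 allocation is assumed. Towns are taken as equal in size.

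**Step 1: which m gives the printed D?** m = 1 + (D − 1)/ρ.
- ICC 0.01: 1 + 0.084/0.01 = 9.40
- ICC 0.05: 1 + 0.419/0.05 = 9.38

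The stated m = 6-8 gives D = 1.05-1.07 and 1.25-1.35. The trial's own 500/80 = 6.25 gives D = 1.0525 and 1.2625. Eight per town in 80 towns would need 640 people. For comparison, 750/80 = 9.375 gives 1.08375 and 1.41875, which round to both printed values, and 750 × 0.8 / 3 is also 200.

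**Step 2: do the detectable differences follow from D?** N_eff = 200/D. For continuous outcomes the detectable difference is (1.960 + 0.8416) × √(2/N_eff) SD. For adherence, the control rate p is solved from the pooled two-proportion formula against 20%.

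| Basis (200 per group) | D at ICC 0.01 / 0.05 | Detectable SD | Control rate vs 20% |
|---|---|---|---|
| Plan as stated | 1.084 / 1.419 | 0.28 / 0.32 | 10.1% / 8.8% |
| Recomputed, printed D | 1.084 / 1.419 | 0.292 / 0.334 | 9.7% / 8.4% |
| m = 6 | 1.05 / 1.25 | 0.287 / 0.313 | 9.8% / 9.0% |
| m = 6.25 | 1.0525 / 1.2625 | 0.287 / 0.315 | 9.8% / 9.0% |
| m = 7 | 1.06 / 1.30 | 0.288 / 0.319 | 9.8% / 8.8% |
| m = 8 | 1.07 / 1.35 | 0.290 / 0.326 | 9.7% / 8.6% |

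The plan's row is not reproduced. The ICC 0.05 end (0.32 SD, 8.8%) fits m = 7. The ICC 0.01 end (0.28 SD, 10.1%) fits no m from 6 to 8.

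**Step 3: power at the stated differences, 200 per group.**

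| Basis | 0.28 SD, ICC 0.01 | 0.32 SD, ICC 0.05 | 20% vs 10.1%, ICC 0.01 | 20% vs 8.8%, ICC 0.05 |
|---|---|---|---|---|
| Printed D | 76.7% | 76.6% | 76.0% | 76.6% |
| m = 6.25 | 77.9% | 81.3% | 77.2% | 81.3% |

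**Step 4: do the outcome ranges share inputs?** With one SD per outcome and the same two ICCs, upper limit/lower limit = √(D at 0.05 / D at 0.01), whatever N or the SD is. Allowing for rounding of the printed limits:
- SD: 0.315/0.285 to 0.325/0.275 = 1.11 to 1.18
- LDL: 8.05/6.75 to 8.15/6.65 = 1.19 to 1.23
- A1c: 0.475/0.415 to 0.485/0.405 = 1.14 to 1.20
- Distress: 4.35/3.75 to 4.45/3.65 = 1.16 to 1.22
- Systolic pressure: 3.5/3.5 to 4.5/2.5 = 1.0 to 1.8, so uninformative

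The LDL and SD intervals do not overlap. A1c and distress each overlap the SD interval.

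**The case against.** **The error may lie in N.** With the printed D and 219 per group, N_eff is 202.0 and 154.3, which gives 0.279/0.319 SD and 10.1%/8.8%. One change therefore recovers all four headline figures, and 0.32/0.28 = 1.143 agrees with √(1.419/1.084) = 1.144. This stands as a possible explanation. It does not rescue the text, which states 200 per group, and it cannot explain LDL, whose ratio does not depend on N.

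**A reader might infer that the lower limits ignore clustering.** At D = 1 and 200 per group the result is indeed 0.280 SD. But 219 per group with clustering fits as well, and the pooled formula at D = 1 gives 10.0%, with 10.1% reached only by the arcsine method. For A1c, systolic pressure, LDL and distress no SD is printed, so no D can be derived for those ranges.

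**A reader might infer a leftover three-arm trial of 750.** The match to 750/80 and the multi-arm wording are consistent with that, but no text available for this check mentions 750 people or a three-arm version.

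**The effect is small and not all in one direction.** This stands. The printed D values are larger than 500 people in 80 towns require. The section also reports ICCs of 0.001-0.015 for most measures in the Encourage study, so 0.05 is cautious.

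**Table 7 may already give more.** The section cites it for detectable adherence differences. It was not in the text available here, so nothing is claimed about which control rates it covers.

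**Conclusion.** The power figures are internally inconsistent and need correction. The printed D values require about 9.4 per town against a stated 6-8. At 200 per group the detectable differences follow neither from those values nor, as a pair, from any m in 6-8. The LDL range comes from different inputs than the SD range.

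The size is modest. On the printed D, power at the stated differences is 76-77%. On the trial's own 6.25 per town, the stated figures are slightly optimistic at ICC 0.01 (about 78% for 0.28 SD, 77% for 20% vs 10.1%) and slightly conservative at ICC 0.05 (about 81% for both). A reader might conclude that the trial is underpowered throughout, but the ICC 0.05 results do not support that.

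These results assume 1:1 allocation, equal towns, exactly 80 towns and m counted at enrolment. More towns would lower D; unequal towns would raise it.

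**What to change.** Recompute the section and Table 7 from one stated set of inputs: two arms, 200 analysed per group, 80 towns, one m, one D per ICC and one printed SD per outcome.

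- With m = 6.25 and equal towns, report about 0.29-0.31 SD and control rates of 9.8% and 9.0% against 20%.
- Say whether m counts enrolled or analysed participants. Analysed m is 400/80 = 5, so D = 1.04 and 1.20, and the range is 0.286-0.307 SD.
- Recompute A1c, systolic pressure, LDL and distress on the same basis.
- Remove the wording about more than one intervention arm.
- Optionally add a labelled sensitivity figure for unequal towns, D = 1 + ρ[(1 + CV²)m − 1], with the CV taken from the 55 Encourage towns. The documents give no CV. At an assumed 0.7-1.0 with ICC 0.05, D is 1.42-1.58 and the limit 0.33-0.35 SD for m = 6.25; for m = 5, D is 1.32-1.45 and the limit 0.32-0.34 SD.

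The cost is a revision of text and table. No patients are added and the design does not change. With equal towns, the ICC 0.01 end becomes slightly less favourable and the ICC 0.05 end slightly more so.
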